It is expected that the mean total daily dose of glucagon will be <1.0 mg daily as in previous studies. The mean daily glucagon dose in our previous 11 day outpatient study was 0.51 mg/day (range 0.20-0.90 mg/day). The recommended dose of glucagon for adult patients suffering from severe hypoglycemia is 1 mg as a single injection. Mean glucagon levels in our previous inpatient studies have been above the normal fasting range for glucagon only 1% of the time. Therefore, the glucagon exposure of subjects is expected to be modest. We expect that glucagon exposure will be the same on both bionic pancreas models.

V. c. Devices

V.c.1. iPhone-based Bionic Pancreas

Infusion sets: Subjects will wear two FDA approved commercially available infusion sets, one for insulin infusion and one for glucagon infusion, when applicable. Infusion sets that are compatible with the Tandem t:slim insulin pump (leur lock connection) will be provided. Note that components of the standard infusion sets are not compatible with DMSO, and therefore this pump cannot be used to pump Xeris glucagon.

Continuous glucose monitors: One transcutaneous glucose sensor for the DexCom G4 Platinum (10) will be inserted in the subcutaneous tissue and will provide input to the controller. The sensor is powered by the battery within the transmitter that clips to the sensor and the whole assembly is held to the skin with an adhesive patch and communicates wirelessly with the G4 receiver. If the G4 sensor fails for any reason during the experiment it will be replaced promptly.

Bionic Pancreas Control Unit: The control unit consists of a stock iPhone 4S and a DexCom G4 Platinum receiver connected with a custom hardware interface and placed back-to-back in a custom enclosure. The G4 receiver converts the raw wireless signal from the transmitter into an estimated BG signal that is sent via a hardwired connection to the iPhone.

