- Study staff will assist the subject to calibrate their CGM, review the study procedures again and assist with the set up of the bionic pancreas system, including inserting and priming infusion sets.
- The control algorithm will be initialized only with the subject's weight. Diagnostics will be performed to ensure that the CGM device is appropriately calibrated and that all of the components of the bionic pancreas systems are in working order.
- The subject's own insulin infusion pump will be stopped and disconnected
- The staff will start the bionic pancreas as close as possible to a minute divisible by 5 minutes (i.e. on a 5-minute mark) and before or at 9:00 AM. The starting time will be considered Hour 0.
- Plasma BGs will be taken off of the IV and measured using the YSI every 15 minutes. Study staff will perform any additional BG check for symptoms of hypoglycemia. There are no restrictions on additional checks.
- The insulin and glucagon infusion sites will be assessed by study staff every 15 minutes for the presence of any moisture and evidence of displacement of the site. The infusion site will be replaced if there is any suspicion of it failing.
- 5 ml plasma samples will be taken and processed every ~30 minutes throughout the experiment for later analysis of insulin and glucagon levels.
- If the IV or YSI fail, capillary BGs using the Nova Biomedical Stat Strip Xpress will be used.
- Additional calibrations will be performed at any of the blood glucose checks throughout the day if the CGM value does not meet the ISO standard (< 15 mg/dl difference for BG values < 75 mg/dl, $< 20\%$ absolute difference for BG values > 75 mg/dL) at the time of the BG measurement AND it is a good time to calibrate (the CGM trend arrow is flat and there has been no carbohydrate intake in the last 30 minutes or glucagon boluses in the last 15 minutes).
- Subjects will be asked to rate any nausea and/or infusion site pain on 10 cm visual analog scales (VAS) at the beginning of the study once the infusion sites have been placed but no drug has yet been administered, then every 2 hours during the study and at the end of the study. Study staff will also evaluate their infusion sites to document any erythema or edema at the same times.

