 - Blood will be drawn for plasma insulin levels then every 30 minutes thereafter until the end of the experiment.
- For the last hour and a half (from 2 to 3.5 hours after injection, t=210 to t=300), blood will be drawn for plasma glucose at least every 30 minutes and for plasma insulin levels every 30 minutes.
- The infusion set site will be assessed for pain, skin reactions, and evidence of failure immediately after insertion, at 1 hour intervals during the experiment, and at the end of each experiment. The participant will complete a short survey evaluating the user experience related to the infusion set at the end of the experiment.
- Three and a half hours after the meal bolus has been given the experiment will end (t=300). The IV will be removed, subjects will switch back to the usual infusion set (and/or pump if applicable) and they will be discharged. Subjects will be advised by a study provider on re-initiation of their own insulin regimen.
- Their basal rates, insulin dose and meal will be the same during both experiments.
- Hypoglycemia will be treated with oral carbohydrates as needed.

V. d. 6. Response to Hypoglycemia

- Subjects are encouraged to check their BG for any symptoms of hypoglycemia.
- Subjects will be permitted to take 15 grams of carbohydrates for any capillary BG value less than 60 mg/dl. Study staff will ensure proper functioning of the bionic pancreas and infusion set, and will encourage the subject to wait for the bionic pancreas to treat the low blood sugar for as long as they feel comfortable.
- Subjects will be required to take 15 grams of carbohydrates for any plasma BG value less than 50 mg/dl. Blood glucose will continue to be checked every 15 minutes per protocol, with increased frequency during exercise. Treatment will be repeated if subsequent BG values are still < 50 mg/dl after 15 minutes. All carbohydrate treatments for hypoglycemia will be documented by study staff (amount and time).
- Study staff will check the infusion site and the bionic pancreas for normal operation any time hypoglycemia occurs. If there is any suspicion of infusion set malfunction, the site should be replaced. Study staff will check the bionic pancreas for any malfunction and correct any problems that are found.
- If no correctable fault is found, but there is doubt regarding the correct function of the bionic pancreas system, an entirely new backup bionic pancreas system may be started.

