- Date of last menstrual period in female subjects
- Date of diabetes diagnosis
- Medical, surgical, and social history, allergies, and review of systems relevant to inclusion and exclusion criteria
- Medications (prescription and non-prescription) and date of last change in medication regimen
- Duration of insulin pump use

- Type of insulin used in pump
- Insulin regimen (basal rate, sensitivity factor, and carbohydrate ratio)
- Average total daily dose of insulin in the last 30 days as available (from pump history)
- Usage of CGM, if any (type of CGM, days per month worn, usage of data, whether insulin is dosed based on CGM alone, alarm settings)
- Height and weight
- Blood pressure
- Hemoglobin A1c
- Urine HCG (pre-menopausal females)
- Fractionated plasma metanephrines (if indicated by history)

VI. a. 2. During study visits:

- CGMG (CGM glucose) every five minutes from the DexCom G4 Platinum CGM
- All BG measurements taken
- Insulin total daily dose
- Glucagon total daily dose
- Timing and content of the meal eaten and carbohydrate amount
- Timing of meal announcement and size of meal announced
- Timing and glucose values at calibrations
- Timing and amount of carbohydrates taken for hypoglycemia
- Time subjects were not under bionic pancreas control for any reason
- List of technical faults associated with the bionic pancreas including cause and resolution
- Nausea on a visual analog scale at study start, every 2 hours, and at study end
- Infusion site pain at study start (after insertion and before any drug administration), every 2 hours, and at study end
- Infusion site reaction according to the Draize scale at study start (after insertion and before any drug administration), every 2 hours, and at study end
- Infusion site appearance every 15 minutes (presence/absence of moisture, evidence site has been displaced)
- Timing of any infusion site replacements
- Subject reports of symptoms of any other complaints
- Timing of exercise and duration
- Volunteer reported Borg scale score for exercise intensity every 5 minutes during exercise
- Heart rate during exercise from Polar heart rate monitor every 5 minutes
- Plasma insulin levels every 30 minutes throughout the experiment
- Plasma glucagon levels every 30 minutes throughout the experiment

VI. a. 3. During the Infusion set Sub-Study:

At Screening:

- Age
- Sex
- Race and ethnicity
- Date of last menstrual period in female volunteers
- Date of diabetes diagnosis

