 - Fraction of time spent within each of the following glucose ranges:
 - < 50 mg/dl.
 - < 60 mg/dl.
 - < 70 mg/dl.
 - 70-120 mg/dl.
 - 70-180 mg/dl.
 - >180 mg/dl.
 - >250 mg/dl.
 - Percentage of subjects with mean CGM glucose < 154 mg/dl (estimated average glucose corresponding to an A1c of 7%).
- Number of severe hypoglycemic events (subject unable to self-treat, requiring the assistance of another person).

During Exercise

- Number of subjects discordant for reaching a BG < 60 mg/dl (measured with YSI) for > 2 consecutive plasma glucose measurements
- Area between the glucose curve and 60 mg/dl calculated from BG measurements
- Area between the glucose curve and 60 mg/dl calculated from CGM data
- Time from start of exercise to first BG measurement < 60 mg/dl
- Time from start of exercise to first CGM measurement < 60 mg/dl

VI. b. 5. Secondary endpoint analyses – Non-glycemic

- Glucagon total delivery per kg of body mass.
- Insulin total delivery per kg of body mass.
- Number of episodes of symptomatic hypoglycemia.
- Number of carbohydrate interventions for hypoglycemia.
- Total grams of carbohydrate taken for hypoglycemia.

- Difference in mean nausea from VAS during the study (mean of measurements every 2 hour and at study end) vs. baseline at study start.
- Difference in Infusion site pain from VAS during the study (mean of measurements every 2 hour and at study end) vs. baseline at study start. Note that in the iLet infusion set the infusion catheters are 1 cm apart, so it may not be possible to differentiate whether a sensation is coming from the insulin or glucagon infusion catheter. Subjects will be asked to use their best judgment and to provide scores for both catheters.
- Difference in local erythema and edema according to the Draize scale (mean of measurements every 2 hour and at study end) vs. baseline at study start. Note that in the iLet infusion set the infusion catheters are 1 cm apart, so it may not be possible to differentiate whether a skin reaction is coming from the insulin or glucagon infusion catheter. Subjects will be asked to use their best judgment and to provide scores for both catheters.
- Number of unscheduled infusion set replacements.
- Number of unscheduled CGM sensor changes.

During Exercise

- Grams of oral carbohydrates given to the subject to treat hypoglycemia
- Total glucagon dosing by bi-hormonal bionic pancreas from the start of exercise until the end of the visit

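### The baseline for site pain and skin reaction is scored after the set is inserted, so in the iLet-versus-iPhone comparison the subtraction can favour the set that hurts more

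*Combined protocol and SAP*

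**What the plan says.** Section VI.b.5 (non-glycemic secondary endpoints) defines two site-tolerability endpoints as change scores, both taken against study start:

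- Pain: "Difference in Infusion site pain from VAS during the study (mean of measurements every 2 hour and at study end) vs. baseline".
- Skin: "Difference in local erythema and edema according to the Draize scale (mean of measurements every 2 hour and at study end) vs. baseline".

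The visit procedures in V.d.4 fix when the study-start score is taken. Subjects rate pain "at the beginning of the study once the infusion sites have been placed but no drug has yet been administered". For the skin, "Study staff will also evaluate their infusion sites to document any erythema or edema at the same times". The data list in VI.a.2 agrees: "Infusion site pain at study start (after insertion and before any drug administration), every 2 hours, and at study end" and, for the skin, "Infusion site reaction according to the Draize scale at study start (after insertion and before any drug administration". No score before insertion is planned.

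The sets differ between platforms. For the iPhone system (V.c.1), "Subjects will wear two FDA approved commercially available infusion sets, one for insulin infusion and one for glucagon infusion". The iLet system (V.c.2) uses a novel steel-cannula set made for that device.

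VI.b.5 does not restrict these endpoints to one comparison. The analysis text that follows it gives a paired t-test or Wilcoxon signed rank test on the endpoints as defined. It adds no comparison of unsubtracted or post-insertion scores.

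**The concern.** A baseline should be measured before the thing being compared can affect it. Here that is true for the drug but not for the set.

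For Xeris versus Lilly glucagon, both given through the iLet set, a score after insertion and before drug is a sensible reference, because it removes insertion trauma and leaves the effect of the infusate. For iLet versus iPhone, the set is part of what differs between the visits. The subtracted score then carries the set's own insertion effect. A set that hurts or reddens more when placed has a larger amount taken off its later scores.

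Aim 1 covers the safety and efficacy of the iLet against the iPhone system, and section I.d gives user safety as one of the grounds on which equivalence is to be established. If the formula is applied to that comparison, a set that scores worse at every time point could be reported as equally or better tolerated, ahead of the larger iLet studies that section I.d foresees.

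**Working it through.** The plan gives no figure for these endpoints, so there is none to reproduce. The check follows from how the score is built.

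**Definitions.** For one subject, compare the two platforms:

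- b = excess of the worse set over the other in the post-insertion score.
- r = share of that excess still present in the mean of the later scores.

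**Formulas.**

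- Difference in post-insertion scores: b.
- Difference in unsubtracted visit means: r × b.
- Difference in the planned change scores: r × b − b = (r − 1) × b.

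The planned endpoint therefore differs from the visit-mean comparison by exactly −b, whatever r is. Pairing does not remove this, because the shift goes with the set within each subject.

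**Worked example (assumed 10 cm VAS scores).**

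| | Post-insertion | Visit mean | Planned endpoint |
|---|---|---|---|
| Commercial set | 1.0 | 0.5 | 0.5 − 1.0 = −0.5 |
| iLet set | 3.0 | 1.5 | 1.5 − 3.0 = −1.5 |
| iLet minus commercial | +2.0 | +1.0 | −1.0 |

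The iLet set is worse in both measured columns and 1.0 cm better on the planned endpoint.

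**Range over r, with b = 2 cm.**

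| r | Visit-mean difference, r × 2 | Planned difference, (r − 1) × 2 |
|---|---|---|
| 0 | 0 | −2.0 |
| 0.25 | 0.5 | −1.5 |
| 0.5 | 1.0 | −1.0 |
| 0.75 | 1.5 | −0.5 |
| 1 | 2.0 | 0 |
| 1.25 | 2.5 | +0.5 |

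Negative values favour the worse set.

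**How r depends on fading.** Suppose the excess decays exponentially and is scored at 2, 4, 6 and 8 hours, taking the 8-hour score as the end-of-study score. Then r is the mean of 0.5^(t/h) over those times, where h is the half-life. For h = 2 hours: r = (0.5 + 0.25 + 0.125 + 0.0625)/4 = 0.234.

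| Half-life (h) | r | Planned difference, b = 2 cm |
|---|---|---|
| 0.5 | 0.017 | −1.97 |
| 1 | 0.083 | −1.83 |
| 2 | 0.234 | −1.53 |
| 4 | 0.453 | −1.09 |
| 8 | 0.661 | −0.68 |

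Even when half the excess is still present at the end of the visit (h = 8), the worse set appears better.

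**Precision.** If the post-insertion score and the visit mean have equal variance s² and correlation ρ (both assumed), the change score for a visit has variance 2s²(1 − ρ). This exceeds s² when ρ is below 0.5, so the subtraction may also add noise.

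**The case against.** The strongest reply is that the endpoint was built for the glucagon comparison. The hypothesis in section II about site reactions concerns Xeris versus Lilly. Aim 2 lists reactions at the glucagon site. The only success criterion in VI.d that names site reactions or pain is Xeris versus Lilly. Aim 1's named secondary outcomes and the main success criterion do not mention them. All of this is correct, and the post-insertion baseline is sound for that comparison. But VI.b.5 does not limit the endpoint to it, the scores are collected at all three bionic pancreas visits, and Aim 1 is stated as a test of safety between platforms.

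A second reply is that Aim 4 exists to isolate the set. In V.d.5, "The infusion set site will be assessed for pain, skin reactions, and evidence of failure immediately after insertion", and VI.b.2 lists pain and skin reactions without subtraction. This shows that unsubtracted scoring is workable. It does not replace the platform comparison: the comparator is Contact Detach on an ordinary insulin pump, over 5 hours and without glucagon.

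Third, poorly tolerated sets would be noticed anyway. Moderate or severe reactions lead to moving the set (V.d.9), persistent ones end participation (IX.b), and unscheduled replacements are counted. These safeguards would catch marked problems but not mild differences, which is what the scales are for.

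Three limits stand. The sizes above are assumed. The reversal requires that the sets differ after insertion and that the excess at least partly fades; if it persists in full the change scores are equal, and if it grows the worse set looks worse. The interval between placement and the first score is not stated, so how much insertion trauma that score captures is unknown. In addition, the earlier set flaws described in section I.d are not said to have been pain or skin reactions, so they add little here.

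**Conclusion.** The concern holds. In the iLet-versus-iPhone comparison, the stated formula subtracts an effect of the device being compared. It shifts the difference in visit means by the full between-set difference in post-insertion score and reverses its sign whenever that excess partly fades. With an assumed 2 cm excess, the worse set appears better by 0.68 to 1.97 cm for half-lives from 8 down to 0.5 hours.

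The weight is moderate. These are secondary endpoints outside the iLet-versus-iPhone success criterion. The Xeris-versus-Lilly comparison, the primary endpoints and the sample size are unaffected. The point is still worth correcting, because the plan's own rule creates the bias and nothing else in the plan offsets it.

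**What to change.** Amend VI.b.5 so that the score follows the comparison:

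- **iLet versus iPhone (both with Lilly glucagon):** use the unsubtracted mean of the 2-hourly and end-of-study scores for pain and for Draize, and report the post-insertion score as a separate outcome.
- **Xeris versus Lilly on the iLet:** keep the change from the post-insertion score.

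In the same edit, state how scores after a mid-visit set replacement are handled. V.d.4 and V.d.9 allow replacement, and trauma from a second insertion would enter the later scores but not the baseline.

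The cost is a wording change and one extra summary row per endpoint. All the scores are already collected, and neither the visit procedures nor the number of subjects changes.

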- If there is an interruption in the Dexcom CGM output, study staff will assist the subject in recovering CGM data streaming. If this requires replacement of the CGM sensor, BGs will continue to be checked every fifteen minutes per protocol. These blood glucoses will be entered into the bionic pancreas, which will treat them as CGM values and dose insulin and/or glucagon appropriately. If the CGM sensor fails a second time, the subject may be asked to repeat that arm of the experiment because of the effect that repeated sensor replacements may have on study outcomes.
- If there is a complete failure of the bionic pancreas operation, subjects will take over their own blood glucose control using their personal insulin pump until the bionic pancreas can be brought back online. If bionic pancreas control cannot be promptly resumed (e.g. within 30 minutes), the subject may be asked to repeat that experiment day.
- Subjects may choose to withdraw from the study at any time. If they withdraw from the study, they should alert a provider immediately.
- The maximum amount of blood loss per visit will be about 120 ml. The maximum amount for the entire study will be about 360 ml.
- After 5:00 PM (at least 8 hours on the bionic pancreas), the bionic pancreas will be stopped and the subject will replace their personal insulin pump.
- Whenever a subject reinitiates their own insulin pump therapy, a study physician will assist the study participants in safely transitioning from control by the bionic pancreas to control using their own insulin pump.
- The bionic pancreas and glucose meters will be collected and downloaded.
- A study MD will review the last several hours of insulin and glucagon dosing and assist the subject in resuming their usual care. They will be instructed to call study staff with any questions, issues or concerns.
- A structured phone interview will be conducted with each participant after they have completed their participation in all bionic pancreas visits. The aim of the interview will be to subjectively compare their experiences with the two systems. This interview will be recorded and de-identified, and will be shared with collaborators.

V. d. 5. Infusion Set Sub-Study Visit Procedures:

- Subjects will arrive at the visit having fasted since 12:00 AM the night before.

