- If a subject experiences a seizure or unconsciousness associated with hypoglycemia, his or her participation in the study will be discontinued.
- In the Infusion Set Sub-Study:
 - Hypoglycemia will be treated at the subject's discretion using oral carbohydrates.
 - If a subject experiences a seizure or unconsciousness associated with hypoglycemia, his or her participation in the sub-study will be discontinued.

V. d. 7. Response to Hyperglycemia

- Study staff will check the infusion site and the bionic pancreas for normal operation any time BG is greater than 300 mg/dl. If there is any suspicion of infusion set malfunction, the site should be replaced. Study staff will check the bionic pancreas for any malfunction and correct any problems that are found.
- If the BG remains > 300 mg/dl for 2 hours despite troubleshooting, blood ketones will be measured. If the blood ketone result is >1.5 mmol/l, the experiment will be stopped and rescheduled. The subject will be provided with insulin and a syringe to give an injection based on their correction factor.
- If no correctable fault is found, but there is doubt regarding the correct function of the bionic pancreas system, the experiment may be stopped and the arm rescheduled.
- If a subject experiences diabetic ketoacidosis, his or her participation in the study will be discontinued.
- In the infusion set sub-study:
 - Study staff will check the infusion site for normal operation and any signs of failure hourly throughout the experiment and any time the BG is greater than 300 mg/dl. If there is any suspicion of infusion set malfunction, the site should be replaced.

- If the BG remains > 300 mg/dl for 2 hours despite troubleshooting, blood ketones will be measured. If the blood ketone result is >1.5 mmol/l, the experiment will be stopped and rescheduled. The subject will be provided with insulin and a syringe to give an injection based on their correction factor.
- If no correctable fault is found, but there is doubt regarding the correct function of the infusion set, the experiment may be stopped and the arm rescheduled.

V. d. 8. Response to Nausea/Vomiting

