The primary analysis of the designated endpoints will be calculated on an intention-to-treat basis. In cases where an arm was not completed (and that arm was not repeated according to protocol criteria) we will use the available data from that arm in the data analysis. We will only include arms that were started by the subject.

We will use the Shapiro-Wilk test to determine the normality of the residuals for each comparison and calculate percentages, means or medians, and standard deviation and/or ranges as appropriate in descriptive analyses. We will use paired t-test or the Wilcoxon signed rank test for comparison of means with normally or non-normally distributed residuals, respectively. In a secondary analysis we will look for any period effect and any interaction between treatment and period, although no such interaction is predicted for the primary outcome, and there is probably insufficient power to identify a small interaction.

VI. c. Power Analysis

The power analysis is based on data from previous studies using the iPhone-based BP. The following table shows the percentage of time that the insulin and glucagon pumps were available to deliver doses calculated by the bionic pancreas. When pumps were not available, this was typically due to loss of communication between the iPhone and the t:slim pumps, but could also be due to pump occlusion or inadequate drug in the reservoir, among many other possible reasons.

Table 1. Time that pumps were available in previous bionic pancreas studies

| Study | insulin | | Glucagon | |
|------------------------------|---------|-----|----------|-----|
| | Mean | SD | Mean | SD |
| Beacon Hill | 96.5 | 2.7 | 95.9 | 2.3 |
| Camp1 | 93 | 2.7 | 92.2 | 2.3 |
| Camp2 | 95.1 | 2.5 | 93.9 | 3.1 |
| Multi-center | 96.1 | 2.5 | 95.9 | 2.5 |
| Mean | 95.2 | 2.6 | 94.5 | 2.6 |
| Min | 93.0 | 2.5 | 92.2 | 2.3 |
| Max | 96.5 | 2.7 | 95.9 | 3.1 |
| ttest (insulin vs. glucagon) | | | 0.044 | |

The glucagon pump was unavailable a greater percentage of the time than the insulin pump in the iPhone-based BP. This could be due to more frequent reservoir changes (the glucagon reservoir had to be changed every day, while the insulin reservoir was changed every other day – the pumps were unavailable during the reservoir change process), greater number of occlusions in the glucagon tubing and infusion sets, or possibly other, unknown factors.

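### The plan does not say whether a visit repeated after device failure keeps its failed first attempt in the reliability analysis, and the natural reading is that it does not

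*Combined protocol and SAP*

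**What the plan says.** Several rules allow a visit to be done again:

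- V. d. 4, complete failure of the system: "If bionic pancreas control cannot be promptly resumed (e.g. within 30 minutes), the subject may be asked to repeat that experiment day".
- V. d. 4, sensor failure: "If the CGM sensor fails a second time, the subject may be asked to repeat that arm of the experiment".
- V. d. 7, if troubleshooting turns up nothing to repair and yet "there is doubt regarding the correct function of the bionic pancreas system, the experiment may be stopped and the arm rescheduled".
- V. d. 7, persistent hyperglycemia: "If the blood ketone result is >1.5 mmol/l, the experiment will be stopped and rescheduled". This one is mandatory.

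V. d. 6 adds that, after hypoglycemia with doubt about the system, "an entirely new backup bionic pancreas system may be started" within the same visit.

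The analysis paragraphs that close section VI. b. call the primary analysis intention-to-treat, limit it to arms the subject began, and say: "In cases where an arm was not completed (and that arm was not repeated according to protocol criteria) we will use the available data".

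The primary endpoint for Aims 1 and 2 (VI. b. 1) is the percentage of algorithm-calculated dose that the pump delivers, for both hormones in Aim 1 and for glucagon in Aim 2. VI. b. 3 adds two measures of the share of 5-minute steps in which the system works as intended, one requiring a fresh CGM reading and one not, and a list of technical faults. VI. a. 2 records "Time subjects were not under bionic pancreas control for any reason". VI. d. ties success to a significant iLet gain on the primary outcome and the associated reliability measures.

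**The concern.** The incomplete-arm rule covers arms that were not repeated. For arms that were, the parenthesis implies that the repeat stands in for the first attempt. The intention-to-treat label and the reference to started arms point the other way, and no sentence settles it. Two analysts could follow the text faithfully and build different datasets.

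For glucose or drug-level endpoints, using the repeat is reasonable. For Aims 1 and 2 the endpoint is whether the device works. If attempts are replaced because the device failed, data are chosen on the outcome, and the device with more replaced failures looks better than it was. Most of the triggers are discretionary. This is the first human test of the iLet, with about ten subjects, so one visit can decide a test. The iLet arm with Lilly glucagon is also the Aim 2 comparator, so a replaced attempt there enters both comparisons.

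**Working it through.** **The plan's own figure.** VI. c. assumes availability of 96% (iPhone) and 98, 99.2 or 99.6% (iLet), SD 2.5, two-sided 5%, 80% power. With n = 2 × (1.960 + 0.842)² × 2.5² / difference² = 98.1 / difference²:

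- difference 2.0: 24.5, so 25
- difference 3.2: 9.6, so 10
- difference 3.6: 7.6, so 8

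These match the stated 25, 10 and 8. The point does not touch them.

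**Which failures reach which measure.** Assume even dosing, an 8-hour visit (480 min, 96 steps) and 99.2% otherwise.

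- Pump unavailable for 2 h, doses still calculated: primary ratio = 99.2 × 360/480 = 74.4%.
- Controller down for 2 h, nothing calculated: numerator and denominator both stop, so the primary ratio stays at 99.2%, whether the attempt is kept or replaced.

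The second kind of failure can show only in the step measures, and only if steps off control are counted.

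**Effect of one kept iLet attempt on a downtime-inclusive measure.** Outage lengths are assumed; 30 min is the plan's example of when a repeat may be requested. Arm value = 99.2 × (480 − lost)/480; mean = (9 × 99.2 + arm value)/10; difference is against 96.

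| iLet outage | Arm value | iLet mean | Difference |
|---|---|---|---|
| replaced | 99.2 | 99.20 | 3.20 |
| 30 min | 93.0 | 98.58 | 2.58 |
| 1 h | 86.8 | 97.96 | 1.96 |
| 2 h | 74.4 | 96.72 | 0.72 |

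Spread grows too. One outlying arm in ten contributes an SD of (99.2 − arm value)/√10. For 1 h this is 12.4/3.162 = 3.92, and √(3.92² + 2.5²) = 4.6 against the assumed 2.5.

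**Chance of a significant iLet advantage.** Simulation with 6,000 trials per setting, 10 pairs, 96 vs 99.2, SD 2.5, Shapiro-Wilk at 5% and then paired t or exact Wilcoxon, two-sided 5%. Columns give the within-subject correlation and whether values are capped at 100.

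| iLet attempt | 0, uncapped | 0, capped | 0.5, uncapped | 0.5, capped |
|---|---|---|---|---|
| replaced | 72.5% | 69.3% | 94.8% | 92.3% |
| kept, 30 min | 42.8% | 32.7% | 63.0% | 44.0% |
| kept, 1 h | 7.7% | 2.4% | 5.0% | 0.9% |
| kept, 2 h | 0% | 0% | 0% | 0% |

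Capping lowers the simulated means to about 98.55 and 95.95, so the true difference in those columns is about 2.6, not 3.2.

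The exact Wilcoxon test shows the mechanism. With ten pairs all favouring the iLet, p = 2/1024 = 0.00195. If the one opposing pair has the largest rank (W = 10), p = 2 × 43/1024 = 0.0840.

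**The other direction.** Replacing one iPhone attempt with a 30 min, 1 h or 2 h outage understates the iLet advantage by 96 × lost/480/10 = 0.60, 1.20 or 2.40 points. The test changes little: 72–96% significant if kept, against 69–95% if replaced.

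**An attempt that stops for good.** If an iLet attempt ends at hour 2, 4 or 6 and all 96 scheduled steps count, it scores 24.8, 49.6 or 74.4%, and the difference becomes −4.24, −1.76 or +0.72. If only steps logged before the stop count, the arm stays at 99.2% and the difference at +3.2.

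**The case against.** - *The primary endpoint is largely untouched.* The clearest trigger is complete system failure, and if nothing is calculated the primary ratio does not move. This stands. A reader might infer that replacement distorts the primary result whenever the device goes down; that holds only for pump-side failures with doses still being calculated.
- *Failures are not hidden.* The fault list is an endpoint, time off control is recorded, and an external board reviews results. This stands, so the plan cannot be said to discard device failures, and no sentence in it does so. But a fault list does not enter the comparison on which VI. d. judges success.
- *The step denominator is already clear.* VI. b. 3 gives the unit and takes data from each visit, and a calculated dose is a condition of correct function, so a step without one ordinarily counts against the device. This mostly stands. What stays open is how to count steps off control or after an early stop.
- *The percentages are soft.* They apply pump-availability values to a different measure, with invented outages, and half of the settings have a smaller true difference because of the cap. This stands; they show sensitivity to one visit, not an expected loss.
- *The bias might be read as favouring the iLet.* The documents give no complete-failure rate for either device, so that inference is unsupported.
- *The infusion set sub-study has a parallel rule* ("there is doubt regarding the correct function of the infusion set, the experiment may be stopped and the arm rescheduled"). Its primary endpoint is insulin exposure rather than device reliability, so the point is confined to Aims 1 and 2.

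**Conclusion.** The concern holds in limited form. The plan leaves the first attempt of a repeated visit without a rule, and its wording leans toward replacement, which for Aims 1 and 2 means selecting data on device failure. The net direction is unknown. The primary ratio is at risk only from failures where doses are calculated but not delivered. Complete controller downtime is visible only in the step measures, and only if time off control and after a device-caused stop is counted.

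As an illustration resting on one assumed 1-hour iLet outage, the VI. c. availability values and ten subjects, keeping instead of replacing the attempt takes the chance of a significant iLet advantage on a downtime-inclusive measure from roughly 70–95% to under 10%. This should be settled before results are seen. It does not undermine the sample sizes or the primary endpoint definition.

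**What to change.** Add to the analysis paragraphs closing section VI. b.: *For all reliability endpoints (VI. b. 1, Aims 1 and 2; VI. b. 3) the first attempt of every started arm is analysed, whether or not it is repeated. Repeats are used for the glycemic and pharmacokinetic endpoints, with first attempts as a sensitivity analysis.*

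Add to VI. b. 3, for the step measure that does not require a new CGM reading: *The denominator is all scheduled 5-minute steps of the visit. Steps off bionic pancreas control because of device failure, or after a stop for device failure or doubt about device function, count as non-functioning. Attempts stopped for other reasons end at the stop and are listed by cause.*

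The cost is a few sentences; time off control and technical faults are already recorded. Reliability figures may be less favourable and more variable: with one iLet arm down 30 min or 2 h and kept, the iLet SD is about 3.2 or 8.2 against 2.5. Attributing a stop to the device needs some judgement. The primary endpoint definition, the VI. c. sample sizes and the clinical rules for stopping or repeating visits stay as they are.
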